3.2 Exclusion Criteria

3.21 All primary cutaneous T-cell lymphomas and Adult T-cell lymphoma/leukemia (HTLV1+)

3.22 Any of the following because this study involves an investigational agent whose genotoxic, mutagenic and teratogenic effects on the developing fetus and newborn are unknown:

- Pregnant women
- Nursing women
- Men or women of childbearing potential who are unwilling to employ adequate contraception

3.23 Co-morbid systemic illnesses or other severe concurrent disease which, in the judgment of the investigator, would make the patient inappropriate for entry into this study or interfere significantly with the proper assessment of safety and toxicity of the prescribed regimens.

3.24 Active, known or suspected autoimmune disease.

Note: Subjects are permitted to enroll if they have vitiligo, type I diabetes mellitus, residual hypothyroidism due to autoimmune condition only requiring hormone replacement, psoriasis not requiring systemic treatment

3.25 Use of systemic treatment with either corticosteroids (>10 mg daily prednisone equivalents) or other immunosuppressive medications <14 days of registration. Note: Inhaled or topical steroids are permitted. >10 mg daily prednisone equivalents are permitted only in adrenal insufficiency in the absence of active autoimmune disease.

- 3.26 Prohibited Treatments and or Therapies
- a) Autologous Stem Cell Transplant (ASCT) ≤ 12 weeks prior to first dose of the study drug.
 - b) Prior treatments (window prior to registration):
 - chemotherapy ≤ 2 weeks
 - nitrosureas ≤ 6 weeks
 - therapeutic anticancer antibodies ≤ 4 weeks
 - radio- or toxin immunoconjugates ≤ 10 weeks
 - radiation therapy ≤ 3 weeks
 - or major surgery ≤ 2 weeks
 - c) Prior treatment with an anti-PD-1, anti-PD-L1, anti-PD-L2, anti-CTLA-4 antibody, or any other antibody or drug specifically targeting T-cell costimulation or immune checkpoint pathways
 - d) Prior treatment with PD1 and PD-L1 inhibiting therapy
 - e) Prior allogeneic SCT
 - f) Chest radiation ≤ 24 weeks prior to registration
- 3.27 Immunocompromised patients, patients with known history of testing positive for human immunodeficiency virus (HIV) or known acquired immunodeficiency syndrome (AIDS) and currently receiving antiretroviral therapy, active Hepatitis B virus surface antigen (HBV sAg+), active Hepatitis C (if Ab+ then PCR+) indicating acute or chronic infection
- 3.28 Uncontrolled intercurrent illness including, but not limited to, ongoing or active infection, symptomatic congestive heart failure, unstable angina pectoris, cardiac arrhythmia, or psychiatric illness/social situations that would limit compliance with study requirements.
- 3.29a Receiving any other investigational agent which would be considered as a treatment for the primary neoplasm.
- 3.29b Other active malignancy ≤ 3 years prior to registration.
EXCEPTIONS: Non-melanotic skin cancer or carcinoma-in-situ of the cervix.
NOTE: If there is a history of prior malignancy, they must not be receiving other specific treatment for their cancer.
- 3.29c Active CNS involvement or leptomeningeal involvement
- 3.29d History of pancreatitis.

4.0 Test Schedule

4.1 Study Calendar

Tests and procedures	Baseline			Active Monitoring Phase			
	≤14 days prior to Registration	≤7 days prior to Registration	Cycle 1 Day 1 prior to treatment	End of each cycle	Restaging End of Cycles 4, 8, and 12	End of Treatment ¹	Observation Post-treatment followup ²
window				±3 days	±7 days	±7 days	±14 days
History and exam, ECOG PS, Weight	X			X ³	X	X	X
Height	X						
Adverse event assessment	X			X	X	X	X
Pregnancy Test ⁴		X	X	X	X	X	X
B Symptoms ⁵	X						
Hematology: CBC with 5 part differential		X		X	X	X	X
Comprehensive metabolic panel: ALT, AST, total bilirubin, alkaline phosphatase, BUN or serum urea, creatinine, Ca, Mg, Na, K, Cl, LDH, glucose, amylase, lipase, albumin, bicarbonate		X		X	X	X	X
Uric Acid		X					
Erythrocyte sedimentation rate	X						
HBV sAg and HCV Ab or HCV RNA	X						
TSH (with Free T4 and Free T3)		X		X ⁶	X	X	X
ECG	X						

¹ At PD or PMD, withdrawal, removal, or completion of protocol therapy

² Four visits: 1) 35±7 days after last treatment 2) 100-120 days post treatment 3) 230-250 days post treatment 4) 330-390 days post treatment

³ If on physical exam there are any palpable lymph nodes present: Tumor (bidimensional)-measurements by physical exam to be done at end of every cycle, prior to next cycle.

⁴ For persons of childbearing potential only: Serum pregnancy testing is required ≤7 days prior to registration and again ≤24 hrs prior to the first infusion, and then every 28 days (±7 days) during the study therapy period regardless of dosing schedule. After discontinuation from nivolumab, these tests should be repeated at approximately 30 days and approximately 70 days [or more frequently if required by local standard].

⁵ Unexplained persistent fever >38° C (or >100.4° F) in previous month, recurring drenching night sweats during the previous month, and/or unexplained weight loss >10% of body weight in the previous six months.

⁶ Thyroid function testing should be done every third month (±3 days).

Tests and procedures	Baseline			Active Monitoring Phase			
	≤14 days prior to Registration	≤7 days prior to Registration	Cycle 1 Day 1 prior to treatment	End of each cycle	Restaging End of Cycles 4, 8, and 12	End of Treatment ¹	Observation Post-treatment followup ²
window				±3 days	±7 days	±7 days	±14 days
PET-CT ⁷	X				X	X	
CT scan Chest/Abd/Pelvis					X ⁸		X
Mandatory research blood/bone marrow samples (See Section 14.0) ^{R,9}			X ^R	X ^R	X ^R	X ^R	X ^{R,10}
Mandatory tissue sample (See Section 17.0) ^{R,11}	X ^R						X ^R

Cycle = 14 days during initial therapy (Cycles 1-8)

Cycle = 28 days during continuation therapy (beginning with Cycle 9)

R Research funded (see Section 19.0)

⁷ Baseline ≤28 days prior to registration, then End of Cycle 4 (≤5 days prior to Cycle 5), end of Cycle 8, and end of Cycle 12

⁸ CT scans after the 12th cycle will be done every 16 weeks as long as treatment continues. Then every 3 months during the first year of observation, then as clinically indicated.

⁹ Must be drawn on Day 1 of each cycle before treatment Cycles 1-4, at restaging post Cycle 12, end of treatment for any reason, and at time of PD or PMD.

¹⁰ Only at time of PD or PMD.

¹¹ Baseline sample to be submitted ≤14 days prior to Registration; see [Section 17.0](#)

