3.0 Patient Eligibility

3.1 Inclusion Criteria

- 3.11 Age \geq 18 years.
- 3.12 Relapsed or refractory T-cell lymphoma (TCL) biopsy-proven \leq 6 months prior to registration, including the following subtypes:
- Peripheral T-cell lymphoma, not otherwise specified
 - Anaplastic large cell lymphoma, ALK negative, primary systemic type
 - Angioimmunoblastic T-cell lymphoma
 - Extranodal NK/T-cell lymphoma, nasal type
 -
 - Blastic NK-cell lymphoma
 - Enteropathy-associated T-cell lymphoma
 - Hepatosplenic gamma delta T-cell lymphoma
 - Transformed mycosis fungoides
 - T/NK-cell lymphoma, unclassifiable
- 3.13 Measurable disease: Subjects must have at least one lesion that is $>$ 15mm (1.5 cm) in the longest diameter on cross-sectional imaging and measureable in two perpendicular dimensions per computed tomography (spiral CT) or MRI.
- 3.14 After failure of ASCT or after failure of frontline therapy in subjects who declined or are not ASCT candidates
- 3.15 ECOG Performance Status (PS) 0, 1 or 2 ([Appendix I](#))
- 3.16 The following laboratory values obtained \leq 7 days prior to registration.
- White blood cell (WBC) \geq 3000/mm³
 - Absolute neutrophil count (ANC) \geq 1500/mm³
 - Platelet count \geq 100,000/mm³
 - Hemoglobin $>$ 9.0 g/dL
 - Total bilirubin \leq 1.5 x upper limit of normal (ULN) unless elevation due to Gilbert's Syndrome
 - Aspartate transaminase (AST) \leq 2.5 x ULN
 - Creatinine \leq 2.0 mg/dL
 - Calculated creatinine clearance must be \geq 45 ml/min using the Cockcroft-Gault formula below:

Cockcroft-Gault Equation:

$$\text{Creatinine clearance for males} = \frac{(140 - \text{age})(\text{weight in kg})}{(72)(\text{serum creatinine in mg/dL})}$$

$$\text{Creatinine clearance for females} = \frac{(140 - \text{age})(\text{weight in kg})(0.85)}{(72)(\text{serum creatinine in mg/dL})}$$

- 3.17 Negative serum or urine pregnancy test done \leq 7 days prior to registration, for persons of childbearing potential only.

Note: Persons of child-bearing potential (POCBP) must use appropriate method(s) of contraception. POCBP should use an adequate method to avoid pregnancy for 23 weeks (30 days plus the time required for nivolumab to undergo five half-lives) after the last dose of investigational drug.

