11.1 Response Considerations

Schedule of Evaluations: PET/CT scans are required at baseline for all patients. In addition to a baseline PET/CT scan, confirmatory scans should also be obtained post Cycle 4, 8, and 12 of chemotherapy, then a CT scan every 16 weeks thereafter. During observation, CT scan should be obtained every 3 months during the first year to evaluate for disease progression.

Definitions for clinical response for patients with lymphoma are from the recently revised Cheson's et al criteria published in 2014, derived from the original criteria published in 2007. (Cheson et al, 2014)(Cheson et al, 2007). Lymph node measurements should be taken from the CT portion of the PET/CT, or other dedicated CT scans where applicable. Measurement of lymphadenopathy for purposes of assessing for PR will be determined by adding the sum of the products of the maximal perpendicular diameters of measured lesions (SPD). The PPD of a single node is sufficient to evaluate for PD (see Table 11.2). Measurable extranodal disease should be assessed in a manner similar to that for nodal disease. For these recommendations, the spleen is considered nodal disease. Disease that is only assessable (eg, pleural effusions, bone lesions) will be recorded as present or absent only, unless, while an abnormality is still noted by imaging studies or physical examination, it is found to be histologically and pathologically negative.

Response is based on PET/CT based on the revised 2014 Lugano Classification. (Cheson et al, 2014).

Progressive disease is based on either PET-CT based (PMD) or CT based (PD) response criteria. PET confirmation of progressive disease is per physician discretion.

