16.2 Statistical Design

16.2.1 Decision Rule

In a previous phase II single arm trial of 130 confirmed PTCL patients receiving Romidepsin (14 mg/m² as a 4 hour transfusion on Days 1, 8 and 15 of 28 day cycles), 25% achieved a response (CR/CRu + PR). The CR/CRu rate was 15%. A second phase II single arm study of 111 treated PTCL patients receiving Pralatrexate (30 mg/m²/wk intravenously for 6 weeks in 7-week cycles) showed a 29% response rate (CR + PR) with 11% having CR. This study will include patients with histologically proven TCL who will be receiving nivolumab (240mg every 2 weeks for 4 months, then 480mg every 4 weeks). It is expected that this dose will have a complete response rate similar to those presented above. The largest success proportion where the proposed treatment regimen would be considered ineffective in this population is 10%, and the smallest success proportion that would warrant subsequent studies with the proposed regimen in this patient population is 30%. This design uses 35 evaluable patients to test the null hypothesis that the true complete response rate is at most 10%.

- 16.2.1.1 Interim Analysis: Enter 12 evaluable patients into the study. If there are one or no successes observed in the first 12 evaluable patients, we will consider this regimen ineffective in this patient population and terminate this study. Otherwise, if the number of successes is at least 2, we will continue accrual.
- 16.2.1.2 Final Decision Rule: If 5 or fewer successes are observed in the first 35 evaluable patients, we will consider this regimen ineffective in this

patient population. If 6 or more successes are observed in the first 35 evaluable patients, we may recommend further testing of this regimen in subsequent studies in this population.

- 16.213 Over Accrual: If more than the target number of patients are accrued, the additional patients will not be used to evaluate the stopping rule or used in any decision making process. Analyses involving over accrued patients are discussed in Section 16.34.

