- 16.214 NOTE: We will not suspend accrual at the interim analysis to allow the first 12 patients to become evaluable, unless undue toxicity is observed. Given the limited overall sample size and the inclusion of an adverse events stopping rule, we feel it is ethical to not halt accrual for the interim analysis. However, if accrual is extremely rapid, we may temporarily suspend accrual in order to obtain safety data on these patients before re-opening accrual to further patients.
- 16.22 Sample Size: This study is expected to require a minimum of 12 and a maximum of 35 evaluable patients. We anticipate accruing 4 additional patients to account for ineligibility, cancellation, major treatment violation, or other reasons. Therefore, the study is expected to accrue a maximum of 39 patients overall.
- 16.23 Accrual Rate and Study Duration: The anticipated accrual rate is 10 evaluable patients per year. Therefore, the accrual period is expected to be 3 years. The primary endpoint will be evaluated approximately 3.5 years after the trial opens, or after the last patient accrued has been observed for at least 6 months and data collection for the induction phase is complete. The total study duration is expected to be approximately 5.5 years, or until all patients have completed all cycles of treatment.
- 16.24 Power and Significance Level: Assuming that the number of successes is binomially distributed, the significance level is .10, i.e. there is a 10% chance of finding the drug to be effective when it truly is not. The probability of declaring that this regimen warrants further study (i.e. statistical power) under various success proportions and the probability of stopping accrual after the interim analysis can be tabulated as a function of the true success proportion as shown in the following table.

If the true success proportion is...	0.10	0.15	0.20	0.25	0.30
Then the probability of declaring that the regimen warrants further study is...	0.098	0.337	0.604	0.795	0.901
and the probability of stopping after the interim analysis is ...	0.659	0.444	0.275	0.158	0.085

- 16.25 Other considerations: Adverse events, quality/duration of response, and patterns of treatment failure observed in this study, as well as scientific discoveries or changes in standard care will be taken into account in any decision to terminate the study
- 16.3 Analysis Plan
 - 16.31 Primary Outcome Analyses:

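### Between Cycle 12 and End of Treatment, and throughout observation, the scheduled imaging is CT of chest, abdomen and pelvis, although nasal-type disease is eligible; silent head or neck relapse can be dated late in PFS and duration of response

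*Combined protocol and SAP*

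**What the plan says.** The PET-CT row of the Study Calendar (4.1) is marked at baseline, at restaging (end of Cycles 4, 8 and 12) and at End of Treatment. Footnote 1 defines End of Treatment as progression, withdrawal, removal or completion of therapy. Footnote 7, attached to the same row, lists baseline and Cycles 4, 8 and 12 but not End of Treatment.

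The other imaging row reads "CT scan Chest/Abd/Pelvis". Footnote 8 sets that CT at every 16 weeks after Cycle 12 while treatment continues. It goes on: "Then every 3 months during the first year of observation, then as clinically indicated". Section 11.1 gives the same intervals ("then a CT scan every 16 weeks thereafter") and names no body region. The observation column carrying the CT mark is defined by footnote 2 as four visits, the first at 35±7 days and the last at 330-390 days, with the middle two given as "2) 100-120 days post treatment 3) 230-250 days post treatment".

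Section 3.12 lists "Extranodal NK/T-cell lymphoma, nasal type" among the eligible subtypes. Section 3.13 asks for one lesion above 15 mm on CT or MRI, wherever it lies. Section 11.3 mentions Waldeyer's ring and prefers target nodes from separate regions of the body.

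Under 16.323 and 16.324, PFS and duration of response are both defined for responders. PFS ends at relapse or death; duration of response ends at the earliest documented relapse.

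**The concern.** CT-based progression in 11.3 rests on growth of an individual lesion from its nadir, or on a new lesion of stated size. Neither can be read in a region that is not scanned. A patient whose target lesion is sinonasal or deep in the neck can enter the trial, respond on PET-CT, and then move to a surveillance scan that, followed as labelled, does not include that lesion.

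Because duration of response stops at the date relapse is documented, a relapse imaged late is dated late. The error runs one way, towards longer duration of response and longer PFS. Both are secondary goals resting on few responders, and 16.331 also uses PFS status and sustained response as outcomes for the correlative analyses.

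**Working it through.** **Background check.** No stated number is in dispute here. The operating characteristics in 16.24 reproduce exactly: P(stop) = P(X1 ≤ 1 | n = 12) and P(declare) = Σ over x ≥ 2 of P(X1 = x) · P(X2 ≥ 6 − x | n = 23). At a true rate of 0.10 these are 0.659 and 0.098; at 0.30 they are 0.085 and 0.901. The goal in 2.1 counts response within 12 cycles, which lies in the period covered by PET-CT, so the point does not touch this design.

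**Imaging gap on treatment** (cycle lengths from 7.11)
- End of Cycle 12: 8×14 + 4×28 = 224 days (32 weeks).
- End of Cycle 32: 8×14 + 24×28 = 784 days (112 weeks).
- Difference: 560 days, or 80 weeks, with 80/16 = 5 surveillance CTs.
- Longest interval between scheduled scans: 16 weeks inside the CT field and 80 weeks outside it. The 80 weeks assumes that the patient completes all 32 cycles, that the End of Treatment PET-CT is done, and that it includes the head and neck (its field is not stated).
- In observation, no scheduled scan outside chest, abdomen and pelvis.

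**Illustration for duration of response.** Assumptions: response at week 8 (end of Cycle 4); exponential true duration with the medians that section 1.1 cites for pralatrexate (10.1 months) and romidepsin (17 months); full treatment; a share f of relapses visible only on PET-CT. The documents do not give f; 5% to 30% is assumed. One month = 30.4375/7 = 4.348 weeks, so the medians are 43.9 and 73.9 weeks, and S(w) = 0.5^(w/median) with w counted from response.

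Twelve months after response is about week 60 of study. The last CT before it is at week 48 (w = 40) and the last PET-CT at week 32 (w = 24). The documented 12-month rate is therefore S(40) if every scan covers all sites, and S(40) + f·[S(24) − S(40)] under the calendar.

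| True median | S(24) | S(40) | Rise at f = 5% | Rise at f = 30% |
|---|---|---|---|---|
| 10.1 months | 0.685 | 0.532 | 0.8 points | 4.6 points |
| 17 months | 0.799 | 0.687 | 0.6 points | 3.3 points |

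A simulation under the same assumptions agrees: 0.531 becomes 0.539 to 0.577, and 0.687 becomes 0.693 to 0.721. The observed median stays at 12.9 months in the first case. In the second it stays at 20.2 months for f up to 10% and moves to the next scan, 23.9 months, for f of 20% or more.

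**Why footnote 7 matters.** At 24 months after response (about week 112) the two schedules agree if the End of Treatment PET-CT is done, because it catches the silent relapses. If it is not done, as footnote 7 alone would read, and such relapses are never otherwise documented, the 24-month excess is f·[S(24) − S(104)]. That is f × (0.685 − 0.194) for the shorter median and f × (0.799 − 0.377) for the longer, or between 2.1 points (longer median, f = 5%) and 14.7 points (shorter median, f = 30%).

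**Observation timing.** The second and third visits are 230 − 120 = 110 to 250 − 100 = 150 days apart, and the third and fourth up to 390 − 230 = 160. Three-monthly scanning means about 91 days.

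**The case against.** The strongest reply is that progression does not depend on this CT alone, and most of that reply stands. Section 11.1 allows progression on PET-CT or CT criteria and takes measurements from other dedicated CT scans where applicable. History and examination are scheduled every cycle on treatment and at every observation visit, and footnote 3 has palpable nodes measured in two dimensions each cycle. Section 18.5 accepts imaging, marrow or pathology reports for progression, and PET-CT is marked at End of Treatment. Palpable neck disease is thus followed, and a symptomatic relapse can be worked up. What is left is silent, non-palpable disease in the sinonasal region or deep neck.

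Three stronger readings are tempting, and the documents support none of them. First, a reader might infer that chest, abdomen and pelvis CT is the only imaging scheduled after Cycle 12; the End of Treatment mark contradicts that. Second, a reader might infer that a target outside the field can never be recorded as progressing, so that PFS and duration of response are in fact overstated. The plan offers the routes just listed, and gives neither the number of nasal-type patients nor the frequency of silent relapse. Third, with 6 to 10 responders (an assumed range), one relapse carries 1/10 to 1/6, or 10 to 17 points, of the Kaplan-Meier curve. That is the weight of any single event in so small a group, not an estimate of bias.

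On timing, it is fair to say that footnote 8 and 11.1 agree with each other and that the CT row's column marks are loose: its other mark sits under restaging at Cycles 4, 8 and 12, while footnote 8 starts after Cycle 12. The mismatch with the four visits is therefore an ambiguity rather than proof that scans would be 150 days apart.

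**Conclusion.** The point holds as a gap in the scheduled field of surveillance imaging. Followed as written, silent head or neck relapse can be dated up to 80 weeks late on treatment, against 16 weeks elsewhere, and has no scheduled scan in observation.

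The consequence is a possible upward bias in two secondary endpoints, confined to responders still free of documented relapse after week 32. Its size cannot be estimated from the documents. The 0.6 to 4.6 points at 12 months rests on the assumed 5% to 30% share, exponential durations borrowed from other agents, and a PET-CT that includes the head and neck. The absence of any difference at 24 months further depends on the End of Treatment PET-CT being done, which the calendar row and footnote 7 leave unsettled. The primary response rate and its decision rule do not change.

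The observation-timing mismatch is real but secondary. It affects the dating of relapse at any site.

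**What to change.** 1. In the CT row of 4.1 and in 11.1, state that surveillance CT covers chest, abdomen and pelvis plus the neck and any baseline-involved site outside that field. This lengthens a scan already scheduled: slightly more radiation and cost in the same session, and no extra visit.
2. Reconcile the End of Treatment mark in the PET-CT row with footnote 7, and state the PET-CT field. This is wording only, unless the scan was not intended or not budgeted.
3. Reconcile the 3-monthly observation CT (footnote 8 and 11.1) with the four visits in footnote 2, so that each scan has a defined time. Three-monthly points (about days 91, 182, 273 and 365) do not all match the visit windows, so this may shift or add a visit.

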1.0 Background

1.1 Disease Background

Non-Hodgkin's lymphomas (NHL) are a heterogeneous group of lymphoproliferative malignancies with differing patterns of behavior and responses to treatment. Like Hodgkin's lymphoma (HL), NHL usually originates in lymphoid tissues and can spread to other organs. NHL, however, is much less predictable than HL and has a far greater predilection to disseminate to extranodal sites. The prognosis depends on the histologic type, stage, and treatment. The NHLs can be divided into two prognostic groups: the indolent lymphomas and the aggressive lymphomas. In Western populations the majority of NHL (~85%) are of B-cell origin.

Approximately 12-15% of the NHL that are not classified as B-cell in origin are T-cell and natural killer (NK) cell in origin. Within these malignancies, two broad groups can be defined, the precursor or pre-thymic lymphomas (e.g. lymphoblastic lymphoma) and the post-thymic lymphomas or peripheral NK/T-cell lymphomas (PTCLs). In the World Health Organization (WHO) Classification, the PTCLs can be further subdivided into predominantly leukemic, extranodal, and nodal types. Studies in recent years have confirmed that lymphomas of the T-cell phenotype have a poorer prognosis than do B-cell lymphomas (Vose, Armitage et al. 2008).

To date, CHOP or CHOP-like chemotherapy has constituted the most prevalent approach to the treatment of PTCLs. However, except for ALK-positive ALCL, this approach has been disappointing both in terms of the response rate and the durability of response. More intensive chemotherapy regimens and stem cell transplantation have been studied, however patient numbers have been small and the populations heterogeneous; none of these approaches have been confirmed to improve outcome in PTCL patients (O'Connor, Bhagat et al. 2014).

In the relapsed and refractory setting, Gemcitabine has been explored both as a single agent and in combination. As a single agent in the relapsed setting, it was associated with a 51% overall response rate (ORR) with 23% complete responses (CR) (Zinzani, Venturini et al. 2010). Bendamustine, as a single agent, was associated with a similar ORR (50%) and CR (28%) with short duration of response (DOR) at 3.5 months and overall survival (OS) of only 6.2 months (Damaj, Gressin et al. 2013). Despite reasonable response rates, the duration of benefit with traditional chemotherapy has been short.

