6.6 Treatment start

Treatment cannot begin prior to registration and must begin ≤ 7 days after registration.

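### The calendar gives two windows for the baseline PET-CT (14 and 28 days), and under the 28-day one permitted prior therapy can fall after the scan, so its effect could be counted as a nivolumab response

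*Combined protocol and SAP*

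**What the plan says.** **Scan window.** In the Study Calendar (4.1) the baseline mark for PET-CT stands in the column headed "≤14 days prior to Registration". Footnote 7, attached to the same row, reads "Baseline ≤28 days prior to registration, then End of Cycle 4". The two cannot both be the limit.

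**Prior-therapy windows.** Section 3.26(b) counts back from registration and excludes "chemotherapy ≤ 2 weeks" and "radiation therapy ≤ 3 weeks". Section 3.26(f) separately excludes "Chest radiation ≤ 24 weeks prior to registration". Antibodies are excluded within 4 weeks and radio- or toxin immunoconjugates within 10 weeks. Section 3.25 excludes corticosteroids above 10 mg prednisone equivalent "or other immunosuppressive medications <14 days of registration", with an allowance for adrenal insufficiency.

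**First dose.** Under Section 6.6 treatment "must begin ≤ 7 days after registration".

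**Response.** The table in Section 11.3 defines a partial response by comparison with baseline: on CT, at least a 50% fall in SPD; on PET, lower uptake than at baseline, with no numeric threshold. Section 16.311 counts any CR or PR during therapy as a success.

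**Order of scan and therapy.** No section requires the baseline PET-CT to follow the last prior therapy, or to be repeated if treatment came in between. Footnote 1 to the table in Section 14.1 does set such a condition, but only for the research biopsy or marrow sample.

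**The concern.** This is a single-arm trial, so the baseline scan is what separates the effect of nivolumab from that of the preceding regimen. If a patient is scanned, then given chemotherapy or radiation, then registered, the first restaging after Cycle 4 compares the disease with an image taken before that treatment. Any shrinkage that persists is credited to nivolumab. A lesion irradiated after the scan could even serve as a target lesion.

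Carry-over of this kind can only add successes. The decision rules are sensitive to small counts: at least 2 of 12 to continue, at least 6 of 35 to recommend further testing. For affected patients, the primary goal in Section 2.1 would not be answered.

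**Working it through.** **Step 1. Overlap in days (registration = day 0).**

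| Prior therapy | Latest permitted day | Days after a day -28 scan | Days after a day -14 scan |
|---|---|---|---|
| Chemotherapy (excluded at 2 weeks or less) | -15 | 28 - 15 = 13 | 0 |
| Non-chest radiation (excluded at 3 weeks or less) | -22 | 28 - 22 = 6 | 0 |
| Steroids above 10 mg (excluded at under 14 days) | -14 | 28 - 14 = 14 | 0 |
| Antibodies (4 weeks), immunoconjugates (10 weeks), chest radiation (24 weeks) | before day -28 | none | none |

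The overlap therefore exists only under footnote 7 and disappears under the column heading. With up to 7 days from registration to first dose, the scan can precede nivolumab by 28 + 7 = 35 days.

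**Step 2. Reproduce the plan's own figures.** Section 16.2 uses n1 = 12 (stop at 1 or fewer), N = 35 (positive at 6 or more) and a null rate of 10%. With success probability p,

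P(go) = Σ over x = 2 to 12 of Bin(x; 12, p) × P(Bin(23, p) ≥ 6 - x).

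This gives 0.0977, 0.3371, 0.6040, 0.7947 and 0.9014 at p = 0.10, 0.15, 0.20, 0.25 and 0.30. Interim stopping is 0.659, 0.443, 0.275, 0.158 and 0.085. All agree with the table in Section 16.24 to rounding (0.4435 against the printed 0.444).

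**Step 3. Add carry-over.** The documents give no figure for its frequency, so two quantities are assumed:
- q: the share of patients treated between the scan and registration;
- c: the share of those who would be scored CR or PR from that treatment alone.

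At a true response rate of 10%, carry-over matters only in the 90% who are true non-responders, so p = 0.10 + 0.90 × q × c. The expected number of false responders in 35 is 35 × 0.90 × q × c.

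| q | c | p | False responders in 35 | P(go) | P(interim stop) |
|---|---|---|---|---|---|
| 0 | – | 0.1000 | 0 | 0.098 | 0.659 |
| 3% | 10% | 0.1027 | 0.09 | 0.107 | 0.647 |
| 5% | 10% | 0.1045 | 0.16 | 0.114 | 0.638 |
| 10% | 10% | 0.1090 | 0.32 | 0.132 | 0.618 |
| 10% | 25% | 0.1225 | 0.79 | 0.192 | 0.558 |
| 10% | 50% | 0.1450 | 1.58 | 0.309 | 0.463 |

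The last row is an upper case. Its c of 50% matches the single-agent response rates of 51% (gemcitabine) and 50% (bendamustine) in Section 1.1. Those come from full treatment, not from what can be given in a 13-day gap.

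**Step 4. After the fix.** If the scan must follow the last chemotherapy or radiation, the 13 and 6 days become 0, so q is 0 for those treatments. The false-positive chance then returns to the stated 0.098, with power 0.901 and N = 35 unchanged.

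**The case against.** The strongest reply is that the route is open on paper but may rarely be used. Patients must have relapsed or refractory disease (3.12), have failed transplant or frontline therapy (3.14) and have a measurable lesion (3.13). Eligibility is judged as of registration (13.7), and Section 18.5 asks for documentation of progression before entry. A patient visibly responding to treatment given after the scan fits poorly with all of this. Carry-over must also still be visible at the first restaging, about 10 weeks after the latest permitted chemotherapy (15 days plus four 14-day cycles is 71 days), and Section 1.1 itself calls the benefit of chemotherapy short. These points stand and argue for small q and c. They do not close the gap, because none of them ties the scan or the progression evidence to the date of the last therapy.

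An old scan can also work against the drug. Disease that grows untreated for up to 35 days before dosing is still compared with the smaller earlier image, which can hide a true response. That stands too. Carry-over acts in one direction, but the net bias of the 28-day window is not established.

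Two stronger readings are tempting. A reader might infer that treatment between scan and registration is likely, because relapsed disease moves fast; no passage supports that or gives any frequency. A reader might also take the radiation window as 3 weeks throughout and antibodies as part of the problem; the 24-week chest rule and the 4-week antibody rule exclude both.

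**Conclusion.** The point holds as a contradiction in the calendar and a missing ordering rule. Followed as written, footnote 7 lets an image taken before chemotherapy or radiation anchor the primary endpoint. The column heading, if applied, would prevent this.

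The size is conditional. At a true response rate of 10%, the false-positive chance goes from 0.098 to 0.107–0.132 when c is 10% and q is 3% to 10%. It reaches 0.192 at q = 10%, c = 25%, and 0.309 in the upper case. These figures rest on assumed q and c and leave out growth before dosing. They do not show that the trial's error rate is inflated to any particular value, only that an average of less than one false responder in 35 is enough to matter. The change is worth making because it is cheap and protects the attribution of response.

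**What to change.** 1. Reconcile the 14-day column with the 28-day footnote in Section 4.1, so that a single baseline PET-CT window remains.
2. State in footnote 7 and Section 11.1 that the PET-CT used as the response baseline must be done after the last prior anticancer therapy (chemotherapy or radiation), and repeated if such therapy came after it. Section 14.1 already sets a comparable condition for the biopsy or marrow sample.
3. Do not use lesions irradiated after the baseline scan as target lesions.
4. Record the dates of the baseline scan and of the last prior therapy, including steroids above 10 mg.
5. Add to Section 16.31 a sensitivity analysis that counts responders treated between the baseline scan and the first dose as non-responders.

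The washout windows and the steroid rule in Section 3.25, including its adrenal-insufficiency allowance, are left unchanged; steroid exposure is handled through items 4 and 5. The decision rules and sample size also stay. The cost is protocol wording, two or three date fields, and a later or occasionally repeated scan in patients treated after their screening imaging.
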